## **15. BLINDING/UNBLINDING**

Blinding is important for the integrity of this clinical study. However, the blind may be broken in the event of a medical emergency in a subject, in which knowledge of the test article identity is critical to the subject's management. Before breaking the blind for a subject, the investigator should determine that the information is necessary (i.e., that it will

alter the subject's immediate management). In many cases, particularly when the emergency is clearly not test article related, the problem may be effectively managed by assuming that the subject is receiving active product without the need for unblinding. The need to break the blind should first be discussed with the responsible Medical Monitor and the best method to do this will be determined.

In Part 1, the test articles will be blinded using color coded labels to designate which test article to apply to each Treatment Area.

## **16. CLINICAL SUPPLIES**

### **16.1 Test Article Information**

Test articles will be packaged and labeled by the Sponsor or designee. Detailed information on the packaging/labeling, blinding/unblinding, storage and preparation, dispensing, accountability etc. is included in [Appendix 3](#).

### **16.2 Supplies Provided by Therapeutics, Inc.**

- CRFs
- Source document draft templates
- Site regulatory binder
- UPT kits
- Digital camera
- Bland emollient (e.g., DML Lotion)

### **16.3 Supplies Provided by Investigator**

- Personal computer to store and view study images
- Urine collection containers for UPTs
- Centrifuge to process blood samples per specifications in laboratory manual (if participating in PK portion of the study)
- Ultra-low freezer for storage of PK blood samples (if participating in PK portion of the study)

### **16.4 Supplies Provided by the Clinical Laboratory**

- Supplies to collect and transport urine and blood samples to the clinical laboratory
- Tubes and labels for plasma aliquots for PK analysis (for sites participating in the PK portion of the study)
- Urine collection containers for urinalysis

## 17. STATISTICAL CONSIDERATIONS

### 17.1 Sample Size

As a first-in-man POC study, no formal power calculations were used to determine the sample size.

### 17.2 Endpoints

#### 17.2.1 Safety Endpoints

Safety endpoints will include:

- Incidence (severity and causality) of any local and systemic AEs
- Number of subjects with presence (and severity) of the following LSRs: stinging/burning, pain, and pruritus at each time point for each Treatment Area collected (summarized by Test Article).
- Changes from Screening in vital signs at Days 29, 57, and 84 (or EOT) (summarized by Treatment Group).
- Changes from Screening in clinical laboratory tests (hematology, chemistry, and urinalysis) at Days 29, 57, and 84 (or EOT) (summarized by Treatment Group).
- UPT results in all WOCBP at Screening, Baseline, Day 29, Day 57, and Day 84 (or EOT).

#### 17.2.2 Pharmacokinetic Endpoints

PK endpoints will include:

- Concentration of isotretinoin and tretinoin pre-dose and at 1, 2, 3, and 4 hours after the first dose on Day 1.
- Trough plasma concentrations ( $C_{12h}$ ) on Days 8, 15, 29, 57, and 84.

#### 17.2.3 Efficacy Endpoints

Part 1 (P1) and Part 2 (P2) efficacy data will be analyzed separately. For Part 1, efficacy endpoints will be summarized by Test Article (PAT-001, 1%; PAT-001, 0.2%; and Vehicle [pooled across Treatment Groups]) and/or by Part 1 Treatment Group (Group 1: PAT-001, 0.1%/Vehicle; and Group 2: PAT-001, 0.2%/Vehicle) as described below. For Part 2, efficacy endpoints will be summarized by Part 2 Summary Group, which consists of four groups:

- Group A: PAT-001, 0.1%-P2 Active/P1 Active
- Group B: PAT-001, 0.1%-P2 Active/P1 Vehicle;
- Group C: PAT-001, 0.2%-P2 Active/P1 Active; and
- Group D: PAT-001, 0.2%-P2 Active/P1 Vehicle.

In Part 1, the following exploratory endpoints will be evaluated:

- Frequency distribution of IGA and CI Signs/Symptoms at Baseline, and Days 8,

- 15, 29, and 57 summarized by Test Article.
- Absolute change from Baseline in IGA and the CI Signs/Symptoms at Days 8, 15, 29, and 57 summarized by Test Article.
  - Within subject difference in IGA and CI Signs/Symptoms at Baseline and Days 8, 15, 29, and 57 summarized by Part 1 Treatment Group.
  - Within subject difference in change from Baseline in IGA and CI Signs/Symptoms at Baseline and Days 8, 15, 29, and 57 summarized by Part 1 Treatment Group.

In Part 2, the following exploratory endpoints will be evaluated:

- Frequency distribution of IGA and CI Signs/Symptoms at Day 84 summarized by Part 2 Summary Group (Group A-D).
- Absolute change from Baseline in IGA and CI Signs/Symptoms at Day 84 summarized by Part 2 Summary Group (Group A-D).
- Absolute change from Day 57 in IGA and CI Signs/Symptoms at Day 84 summarized by Part 2 Summary Group (Group A-D).
- Within subject difference in IGA and CI Signs/Symptoms at Day 84 summarized by Part 2 Treatment Group (0.1% and 0.2%).
- Within subject difference in absolute change from Baseline in IGA and CI Signs/Symptoms at Day 84 summarized by Part 2 Treatment Group (0.1% and 0.2%).
- Within subject difference in absolute change from Day 57 in IGA and CI Signs/Symptoms at Day 84 summarized by Part 2 Treatment Group (0.1% and 0.2%).

### **17.3 Statistical Methods**

Summary tables (descriptive statistics and/or frequency tables) will be provided for screening variables, baseline variables, efficacy variables, and safety variables. Continuous variables will be described by descriptive statistics (n, mean, median, standard deviation, minimum, and maximum). Frequency counts and percentage of subjects within each category will be provided for categorical data.

#### **Study Populations:**

The Safety population will include all enrolled subjects who applied the test article. The intent-to-treat (ITT) population will include all randomized subjects who were dispensed the test article. The PK population will include those subjects in the Safety population who participated in the PK portion of the study with no evidence of material dosing noncompliance.

#### ***17.3.1 Safety Analyses***

The analysis of safety will be conducted on the Safety population.

#### Extent of Exposure

Extent of exposure will be calculated separately for Part 1 and Part 2 and overall. The total amount of each test article used by each subject (difference between the weight of the tubes dispensed and weight of the tubes returned) and the mean daily amount of test article applied (total amount of test article used divided by the number of days dosed) will be calculated for each Treatment Group and Test Article. Descriptive statistics will be used to summarize the total amount and mean daily amount of test article applied.

#### Adverse Events

All AEs reported during the study will be listed, documenting onset, severity, whether therapy was required, any change in test article dosing, investigator assessment of the relationship to the test article, and outcome. AEs will be coded using MedDRA using preferred terms (PTs) and system organ class (SOC). The PTs and SOC will then be tabulated. All treatment emergent AEs (TEAEs) will be summarized by the number of subjects reporting AEs, SOC, PT, severity, and relationship to test article.

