### **4. STUDY DESIGN**

This is a two part, Phase 2, multicenter, proof-of-concept (POC) study of the safety and tolerability of PAT-001 for the treatment of CI in subjects 12 years of age and older. Part 1 will be a double-blind, randomized, vehicle controlled, bilateral comparison, and Part 2 will be a double-blind, active only treatment comparison of the two PAT-001 concentrations. Subjects will have the option to participate in the PK portion of the study. Approximately 18 subjects will be enrolled at three study sites.

Subjects will be randomized (1:1) to one of two Treatment Groups:

- Group 1: PAT-001, 0.1% vs. vehicle
- Group 2: PAT-001, 0.2% vs. vehicle

Subjects will have two comparable Treatment Areas defined per protocol. Each Treatment Area must be comparable in size, with a minimum of 150 cm^2 of affected diseased skin with an identical Investigator’s Global Association (IGA) score, with a score of either 3 (moderate) or 4 (severe) at Baseline; each Treatment Area shall be contained within a discrete anatomic unit as defined in the protocol and shall not exceed 6% body surface area (BSA), excluding palms and soles. In Part 1, one Treatment Area (e.g., right side) will be randomly designated to be treated with one “active” test article (i.e., PAT-001, 0.1%, or 0.2%) and the other Treatment Area (e.g., left side) will be assigned the second test article (i.e., vehicle). Treatments will be applied twice daily for eight weeks to all disease affected skin in the Treatment Area. In Part 2, both Treatment Areas (i.e., right and left sides) will be treated with the “active” test article (i.e., PAT-001, 0.1% or 0.2%) of the assigned Treatment Group twice daily for an additional four weeks.

Subjects will have seven clinic visits and two phone calls. Safety, tolerability, and efficacy measures will be evaluated by Test Article, Treatment Group, within subjects, and by Summary Group as applicable (see [Section 17](#)). Pharmacokinetic (PK) measures of

isotretinoin and tretinoin will be compared to background systemic retinoid levels pre- and post-treatment for each Treatment Group in an optional PK portion of the study.

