Modifications to the dosing regimen and/or concomitant medication/therapy use may be prescribed by the investigator to manage intense LSRs and must be documented in the CRFs. **Any dosing modifications or changes to concomitant medications/therapies will be made bilaterally (e.g., if dosing is decreased to once a day given tolerability issues, both sides will be treated once daily, even if only one side is having the tolerability issue).** Frequency of dosing may be reduced to once per day (QD) or rest periods of up to several days may be allowed. Treatment per protocol should resume as soon as possible after any notable LSRs have materially subsided as determined by the investigator or designee (if possible via one of the scheduled clinic visits or via an Unscheduled Visit) such that dosing may resume. Additionally, use of provided bland emollient in the Treatment Areas as an aid to managing LSRs may be prescribed with the approval of the investigator and must be documented in the CRFs. In the event that additional moisturizer use is needed (i.e., greater than QD or twice a day (BID) or in lieu of the test articles) in the opinion of the investigator, such therapy may be used, must be documented in the CRFs, and the investigator must notify the Medical Monitor promptly. Note: Bland emollients should not be applied within four hours of application of the test articles. No other topical therapy within the Treatment Area or in the surrounding skin within one inch of the Treatment Area is permitted.

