Test article is defined as a pharmaceutical form of an active ingredient (or "primary operational component" for devices) or vehicle/placebo being tested or used as a reference in the study, whether blinded or unblinded. AEs may be either spontaneously reported or elicited during questioning and examination of a subject. All AEs must be completely recorded on the AE CRF. If known, the investigator should report the diagnosis of the underlying illness or disorder, rather than its individual symptoms. Subjects experiencing AEs that cause interruption or discontinuation of test article, or those experiencing AEs

that are present at the end of their participation in the study should receive follow-up as appropriate. If possible, report the outcome of any AE that caused permanent discontinuation or that was present at the end of the study particularly if the AE is considered by the investigator to be treatment-related (i.e., definitely, probably, or possibly related to test article).

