#### Local Skin Reactions

Severity of LSRs (stinging/burning, pain, and pruritus) will be recorded for each Treatment Area (i.e., Test Article). LSRs will be summarized by frequency and severity of each individual LSR at each visit.

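### The adverse event tables in Section 17.3.1 name no affected side, Test Article, Treatment Group or Part, so local reactions captured only as AEs get no planned active–vehicle comparison

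*Combined protocol and SAP*

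**What the plan says.** Section 17.2.1 gives the AE endpoint as "Incidence (severity and causality) of any local and systemic AEs", with no grouping attached. Section 17.3.1 then describes a listing: "All AEs reported during the study will be listed, documenting onset, severity, whether therapy was required, any change in test article dosing", followed by the causality rating and the outcome. For the tables it says "All treatment emergent AEs (TEAEs) will be summarized by the number of subjects reporting AEs, SOC, PT, severity, and relationship to test article". The synopsis uses the same wording.

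The neighbouring measures do have a grouping. Local skin reactions (LSRs) are reported "at each time point for each Treatment Area collected (summarized by Test Article"), and 17.3.1 adds that "LSRs will be summarized by frequency and severity of each individual LSR at each visit".

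Section 4 states a general intention: "Safety, tolerability, and efficacy measures will be evaluated by Test Article, Treatment Group, within subjects, and by Summary Group as applicable". It refers the reader to Section 17 for the detail.

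Section 10.4 decides what reaches the AE form. Burning/stinging, pain and pruritus are graded per Treatment Area at clinic visits. They become AEs only if they need medical intervention or lead to withheld or less frequent dosing. Every other local reaction goes straight to the AE form.

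**The concern.** The design randomises the two sides of each subject to active and vehicle for eight weeks, so every local reaction in Part 1 has its own vehicle control on the same person. The AE tables as written do not use that control. They count subjects, and in Part 1 every subject is exposed to both ointments.

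The AE period in Section 14 runs from the first dose to the final visit. A single TEAE table therefore also pools the eight vehicle-controlled weeks with the four weeks of Part 2, when both sides receive active ointment.

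Safety and tolerability is the primary objective, AE incidence is the first safety endpoint listed, and Section 14.1 says the ointment has not been studied in humans before. For a reaction that reaches the report only as an AE, the reader would learn how many subjects had it, but not whether it occurred on the active or the vehicle side.

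**Working it through.** The documents give no power, alpha or event-rate figure on this point, so there is none to reproduce.

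**Step 1. The split stated for each measure.**

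| Measure | Section | Stated split |
|---|---|---|
| LSRs (burning/stinging, pain, pruritus) | 17.2.1, 17.3.1 | Treatment Area and Test Article, by visit |
| Vital signs, laboratory tests | 17.2.1 | Treatment Group |
| Extent of exposure | 17.3.1 | Part, Treatment Group, Test Article |
| IGA, erythema, scaling, fissuring, papulation/lichenification | 17.3.2 | Part; in Part 1 also Test Article and within-subject difference |
| AEs and TEAEs | 17.2.1, 17.3.1 | None |

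Section 4's intention is carried out for every row except the last.

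**Step 2. Can the missing splits be derived from fields the documents name?**

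- Treatment Group: yes, from the randomisation.
- Part: mostly, by setting AE onset against the application dates on the CRF (Appendix A 3.6) and the application times in the Subject Diary (Section 6.2, Appendix 2).
- Side: no. The causality rating does not give it, because Section 14 defines test article to include "vehicle/placebo being tested or used as a reference in the study, whether blinded or unblinded". A dosing change does not give it, because under Section 6.2 "Any dosing modifications or changes to concomitant medications/therapies will be made bilaterally". The diary's right and left boxes record where ointment was applied, not where a reaction occurred. Photographs may document AEs, but Section 11 rules them out for grading or other assessment.

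**Step 3. Which reactions are affected.** Section 14.1 lists the common reactions to topical retinoids.

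- Burning, stinging, pain or tenderness, and pruritus are covered at visits by the LSR tables.
- Erythema and exfoliation (scaling) have an active-minus-vehicle difference in 17.3.2, though as efficacy signs.
- Irritation, dryness, pigment change and photosensitivity remain, with no by-side summary.

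**Step 4. A subject count does not identify the difference.** Let p_a and p_v be the rates of a local event on the active and vehicle sides. Assume, for illustration, that sides are independent. The proportion of subjects with any event is 1 − (1 − p_a)(1 − p_v).

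| p_a | p_v | Subjects with any event | Active minus vehicle |
|---|---|---|---|
| 50% | 0% | 1 − 0.5 × 1 = 50% | +50 points |
| 40% | 16.7% | 1 − 0.6 × 0.833 = 50% | +23.3 points |
| 29.3% | 29.3% | 1 − 0.707 × 0.707 = 50% | 0 points |
| 0% | 50% | 1 − 1 × 0.5 = 50% | −50 points |

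All four give the same expected count, 9 of 18. A Treatment Group column does not help, because each subject in either group has both an active and a vehicle side.

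**Step 5. Size in a group of about 9.** If k of n subjects have a one-sided event and a of those are on the active side, the difference is (a − (k − a))/n = (2a − k)/n. With side unknown, a can be anything from 0 to k, so the difference lies between −k/n and +k/n. For n = 9:

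- k = 1: ±1/9 = ±11 points
- k = 2: ±2/9 = ±22 points
- k = 3: ±3/9 = ±33 points

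The values of k are assumed.

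**Step 6. LSRs that become AEs between visits.** Part 1 LSR grading falls on Days 1, 8, 15, 29 and 57, so the gaps are 7, 7, 14 and 28 days. With the windows of 29±3 and 57±4, the last gap runs from 53 − 32 = 21 to 61 − 26 = 35 days. The Visit 7 call on Day 43±3 falls inside it, nominally 14 days from each end, and asks about AEs. Sections 6.2 and 9 also provide for Unscheduled Visits to document tolerability problems. This is a smaller and partly covered portion of the gap.

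**Step 7. What by-side tables would hold.** Part 1 would have about 9 areas on 0.1%, 9 on 0.2% and 18 on vehicle, 36 in all, giving about 9 within-subject pairs per group.

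**The case against.** The strongest reply is that the AE CRF is not among the documents and may record the affected area. Section 17.3.1 describes a listing and a summary and does not claim to specify the form. Section 4 already commits to evaluation by Test Article and within subjects, and Treatment Group and Part can be added when the tables are built. The remaining reactions are few, the trial is descriptive with about 9 subjects per group, and no hypothesis test is affected.

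Much of this stands, and it limits the point. It does not remove it. Even if the CRF captures side, 17.3.1 plans no table that uses it, and Section 4 hands the detail to a section that does not supply it for AEs. Descriptive counts by side are what the plan already gives for LSRs, so asking for them here adds no testing.

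Three stronger readings are tempting, and the documents do not support them:

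- A reader might infer that side is lost. The documents show only that no named AE field carries it. The form, or an incidental mention in the reported term, may do so.
- A reader might infer that local tolerability has no active–vehicle comparison at all. Steps 1 and 3 show otherwise.
- A reader might infer that Part 1 and Part 2 applications can fall on the Visit 8 day with no times recorded, so that events that day cannot be assigned to a Part. Sections 9.2 and 9.4 tell subjects to hold application on clinic-visit days. The Visit 7 call in Section 9.3 repeats this for the morning dose, and Section 6.2 bars PK subjects from applying before Visit 8. A same-day Part 1 application would depart from those instructions. The diary records application times; only the first and last application entries on the CRF are described by date alone. What remains is that AE onset is not stated to include a time.

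**Conclusion.** The point holds as an omission in the AE tables, and the plan should be changed. Followed as written, 17.3.1 gives no Part 1 active–vehicle comparison for local reactions captured only as AEs, mainly irritation, dryness, pigment change and photosensitivity. LSRs that become AEs and resolve between visits are a lesser part of it.

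Confidence is high that the table specification lacks these splits, because that is read directly from the text. Whether side could be recovered afterwards is open, because it depends on a form that was not supplied. The ±11, ±22 and ±33 point ranges assume 9 subjects, one to three one-sided events and no knowledge of side, and they shrink to nothing if side is recorded. They show the possible size of the ambiguity and do not predict it.

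**What to change.** 1. Confirm that the AE CRF records the affected area (right, left, both, not local). Add the field if it is absent, because side is best captured when the event is recorded.
2. In 17.3.1, tabulate Part 1 application-site TEAEs by the Test Article on the affected area (0.1%, 0.2%, vehicle). Within each Treatment Group, add within-subject counts: active only, vehicle only, both, neither. Another paired layout would serve if it keeps the same information.
3. Tabulate Part 2 application-site TEAEs separately, with a note that there is no concurrent vehicle.
4. Tabulate all other TEAEs by Treatment Group within Part.
5. Assign Part by onset relative to the first Part 2 application, with a before/after flag for events on the day of Visit 8.
6. Make the same change in the synopsis.

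The cost is at most one or two CRF fields, a few sentences in 17.3.1 and some re-cut tables. No visit or procedure is added.

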#### Local Skin Reactions

Severity of LSRs (stinging/burning, pain, and pruritus) will be recorded for each Treatment Area (i.e., Test Article). LSRs will be summarized by frequency and severity of each individual LSR at each visit.

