Visit Number	Screening 	Part 1							Part 2
	1	2	3 	4	5	6	7 	8	9
Visit Type	Clinic	Clinic	Phone	Clinic	Clinic	Clinic	Phone	Clinic	Clinic
Day	-45 to -7	1	2	8+1	15±2	29±3	43±3	57±4	84±4
LSR		X  Pre&Post		X	X	X		X  Pre&Post	X
Photography		X		optional	optional	X		X	X
PK Blood Draws (optional)		X  Pre, 1, 2, 3, & 4 hr		X 	X 	X 		X 	X 
Randomization	X 	X							
Part 1: Dosing at the Clinic		X		X 	X 	X 			
Part 2 Dosing & Per Protocol Instructions								X 	
Test Articles Accountability: Dispense/Collect/Weigh –Part 1 Dosing		X		X	X	X		X	
Test Articles Accountability: Dispense/Collect/Weigh – Part 2 Dosing								X	X
Compliance / Diary Review 		X	X	X	X	X	X	X	X
Concomitant Medications and Therapies	X	X	X	X	X	X	X	X	X
Adverse Events		X	X	X	X	X	X	X	X

 LSRs will be evaluated pre- and post-test article application on Day 1 and Day 57.

 On Day 1, PK blood samples will be collected for isotretinoin and tretinoin pre-test article application (time 0) and at 1, 2, 3, and 4 hours post-application.

 On Days 8, 15, 29, 57, and 84, a PK blood sample will be collected for isotretinoin and tretinoin pre-test article application (approximately 12 hours ± 30 minutes after the last test article application on the previous day).

 Prior to Visit 2/Baseline, after laboratory results have been received and reviewed, a randomization request will be placed by the site in order for the test article to be provided to the site prior to baseline. Note: the ordered test article is specific to each subject and shall not be used for any other subject.

 If possible, the subject will apply one of the daily doses in the clinic under staff supervision to reinforce proper use.

 In Part 2, subjects will enter an active only treatment follow-up period of four weeks in which both Treatment Areas identified in Part 1 will be treated with the active test article of their assigned treatment group.

 Subject Diary will be reviewed; compliance will be discussed based on review of Subject Diary and Test Article Accountability, as applicable.

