### **3. OBJECTIVE**

The primary objective is to investigate the safety and tolerability of topically applied PAT-001 as a treatment for CI of either the Lamellar or X-Linked subtypes.

The secondary objectives are (1) to explore evidence of a potential efficacy signal of the “active” test article (i.e., PAT-001, 0.1% and 0.2%) compared to vehicle and (2) to explore the plasma levels of isotretinoin and tretinoin from topically applied PAT-001 with comparison to background systemic retinoid levels pre- and post-treatment.

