### ***5.1.3 Subject Withdrawal Criteria***

Procedures for handling subjects who are discontinued from the study are described in [Section 13.2](#). Subjects who are discontinued will not be replaced.

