### 10.4 Local Skin Reactions

At each clinic visit (except Visit 1/Screening), LSRs including burning/stinging, pain, and pruritus will be documented in each Treatment Area using a four-point ordinal scale where 0=none, 1=mild, 2=moderate, and 3=severe. These LSRs will be collected independently

of AEs. Only LSRs that require medical intervention (e.g., prescription medication) or require withholding or reduction in dosing frequency of the test articles will be documented as AEs. Any LSRs that are not listed above will be recorded as AEs.

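### Local skin reactions are summarised only visit by visit, so the plan gives no cumulative subject-level reaction rate by Test Article, and the visit tables cannot supply one

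*Combined protocol and SAP*

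**What the plan says.** Section 3 sets the aim: "The primary objective is to investigate the safety and tolerability of topically applied PAT-001". Section 10.4 scores burning/stinging, pain and pruritus in each Treatment Area on a "four-point ordinal scale where 0=none, 1=mild, 2=moderate, and 3=severe". A Schedule of Events footnote adds that "LSRs will be evaluated pre- and post-test article application on Day 1 and Day 57".

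The endpoint in 17.2.1 is "Number of subjects with presence (and severity) of the following LSRs: stinging/burning, pain, and pruritus at each time point for each Treatment Area collected", summarised by Test Article. The analysis in 17.3.1 matches it: "LSRs will be summarized by frequency and severity of each individual LSR at each visit". The synopsis (Study Endpoints, Statistical Methods) says the same. Neither the synopsis nor section 17 plans a worst post-application grade, a count of subjects ever affected, or a rule for LSR scores that are missing after discontinuation.

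Three other provisions bear on the point:
- Under 10.4, an LSR also becomes an adverse event (AE) if it needs medical intervention, or if dosing is withheld or made less frequent. Under 17.3.1, treatment-emergent AEs are counted by subject.
- Visit 9 doubles as the early-termination visit and scores LSRs in both areas (9.7). Sites are asked to bring leavers back for final procedures (13.2).
- Section 5.1.3: "Subjects who are discontinued will not be replaced".

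**The concern.** Topical irritation can come and go, and different subjects can react at different visits. A set of visit tables shows the prevalence at each assessment. It does not show how many subjects had at least one moderate or severe reaction on a given strength, because nothing tells the reader whether the same or different subjects are counted in successive rows.

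That cumulative count is a natural summary for a tolerability objective. LSRs are also the safety measure that 17.2.1 explicitly assigns to Treatment Area and Test Article, so they carry the within-subject active-versus-vehicle comparison that the bilateral design provides. The study has no formal hypothesis test or model that would combine the visits. The tables named in the plan are therefore what readers will use to judge the two concentrations.

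**Working it through.** The plan states no LSR rate, drop-out rate or power, so there is no figure to reproduce beyond 2 × 9 = 18 subjects. All rates below are illustrative.

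**Inputs.** About nine subjects per Treatment Group (synopsis). From the Schedule of Events, the Part 1 scores after first application are Day 1 post, Day 8, Day 15, Day 29 and Day 57 pre, which makes 5. Part 2 has Day 57 post and Day 84, which makes 2.

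**Bounds on the number ever affected.** If k of n subjects are affected at each of 5 scores, the number ever affected lies between k (always the same subjects) and min(n, 5k) (as little overlap as possible).
- One concentration, n = 9, k = 1: every row reads 1/9 = 11.1%. Ever affected: 1/9 (11.1%) to 5/9 (55.6%).
- n = 9, k = 2: every row reads 22.2%. Ever affected: 2/9 (22.2%) to 9/9 (100%).
- Vehicle pooled over both groups (assumed), n = 18, k = 1: every row reads 5.6%. Ever affected: 1/18 (5.6%) to 5/18 (27.8%).

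These bounds need no model; they follow from the table format.

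**A midway case.** If reactions were independent between assessments, the ever-affected rate would be 1 − (1 − p)^5:
- p = 5%: 1 − 0.95^5 = 22.6%
- p = 10%: 1 − 0.90^5 = 41.0%
- p = 20%: 1 − 0.80^5 = 67.2%

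With complete persistence the rate is p itself. At an assumed 10% per assessment, these two cases give 10% and 41%.

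**Leavers.** Suppose d of 9 subjects leave after a moderate or severe reaction at Day 8 and nobody else reacts. If percentages use only those still attending, which the plan does not say, then:
- d = 1: Day 57 reads 0/8; ever affected 1/9 = 11.1%
- d = 2: Day 57 reads 0/7; ever affected 2/9 = 22.2%
- d = 3: Day 57 reads 0/6; ever affected 3/9 = 33.3%

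The Day 8 row still shows d/9 in each case.

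**Can the AE table fill the gap?** Four points, side by side:
- *Trigger.* A grade 2 or 3 LSR managed without medical intervention or a dosing change does not become an AE (10.4).
- *Scale.* AE severity is graded by interference with usual activities (14.1), not on the 0–3 LSR scale.
- *Split.* The AE paragraph of 17.3.1 does not say that events are divided by Test Article or Treatment Area.
- *Consistency.* The synopsis (Study Measurements) names medical intervention and withholding as triggers; 10.4 adds reduced dosing frequency. A reaction handled only by less frequent dosing is an AE under one text and not under the other.

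**Can the early-termination score fill it?** The vital-sign and laboratory endpoints in 17.2.1 provide for an end-of-treatment value at the last time point; the LSR endpoint does not. No visit row is named for an early-termination LSR score. If a Part 1 leaver's score were placed at Day 84, a vehicle-treated area would appear in a row where both areas are meant to be on active treatment.

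**The case against.** The strongest reply is that the reactions that matter most are already captured. An LSR bad enough to require treatment or withholding becomes an AE, is counted once per subject with its severity, and is listed with any dosing change and its outcome. Leavers should have a final LSR score, their earlier scores stay in the earlier rows, and withdrawal due to an AE is a recorded reason. Section 6.2 also provides reduced frequency, rest periods and emollient, which may limit withdrawals. This stands. A reader might infer that the trial will never report intolerant subjects, or that those who leave disappear from the results. The documents support neither reading.

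It is also fair to say that endpoint and analysis agree with each other, that the study is small and descriptive, and that section 3 does not define tolerability as a proportion of subjects. The per-visit choice is therefore not an internal contradiction.

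A third reply concerns the remedy. Section 1 lists pruritus among the symptoms of ichthyosis itself, so a bare worst-grade count would label stable baseline itch as a reaction. That is correct, and the summary has to use the Day 1 pre-application score.

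The AE route nevertheless leaves out moderate and severe LSRs managed without intervention or a dosing change, and it does not secure the comparison by Test Article.

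**Conclusion.** The point holds in a limited form. The plan contains no cumulative subject-level LSR summary by Test Article, and its visit tables cannot yield one: a constant 1/9 across five Part 1 scores fits 11% to 56% ever affected. The upper end requires a different subject at each score, so it is a bound and not a forecast.

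A reader might go further and conclude that late-visit tables are biased towards good tolerability. The documents do not establish that. Denominators of attending subjects and the drop-out scenarios above are assumptions; the plan places safety analyses on the Safety population and is silent on missing LSR scores. If percentages do use only attending subjects, late rows would understate intolerance when intolerant subjects leave. What can be said now is that the rule is missing.

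This should be corrected. It is a moderate reporting gap on the primary objective, not an error in any stated figure.

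**What to change.** In the synopsis, 17.2.1 and 17.3.1:

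1. For each LSR and Treatment Area, add the number and percentage of Safety-population subjects by worst post-application grade, and by worst grade that exceeds the Day 1 pre-application grade.
2. Show active and vehicle areas within each Treatment Group, separately for Part 1 (Day 1 post to Day 57 pre) and Part 2 (Day 57 post to Day 84).
3. Include early-termination scores and any recorded unscheduled scores, assigned to the Part in which the subject was last treated.
4. Keep the by-visit tables as the time course, and print the number assessed at each visit.
5. Reconcile the LSR-to-AE trigger between the synopsis and 10.4.

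The cost is one extra table and a few lines of text, from data already collected. On the same denominator, the worst-grade rate will be at least as high as the rate at any single visit, so the headline may look less favourable.
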